1. DIAGNOSIS VERSUS SIGNS AND SYMPTOMS

1.1. INFUSION-RELATED REACTIONS

Adverse events that occur during or within 24 hours after study drug administration and are judged to be related to study treatment infusion should be captured as a diagnosis (e.g., infusion-related reaction or anaphylactic reaction) on the Adverse Event eCRF. If possible, avoid ambiguous terms such as “systemic reaction”. Associated signs and symptoms should be recorded on the dedicated Infusion-Related Reaction eCRF. If a participant experiences both a local and systemic reaction to the same dose of study drug, each reaction should be recorded separately on the Adverse Event eCRF, with signs and symptoms also recorded separately on the dedicated Infusion-Related Reaction eCRF.

1.2. OTHER ADVERSE EVENTS

For adverse events other than infusion-related reactions (see Section 1.1), a diagnosis (if known) should be recorded on the Adverse Event eCRF rather than individual signs and symptoms (e.g., record only liver failure or hepatitis rather than jaundice, asterixis, and elevated transaminases). However, if a constellation of signs and/or symptoms cannot be medically characterized as a single diagnosis or syndrome at the time of reporting, each individual event should be recorded on the Adverse Event eCRF. If a diagnosis is subsequently established, all previously reported adverse events based on signs and symptoms should be nullified and replaced by one adverse event report based on the single diagnosis, with a starting date that corresponds to the starting date of the first symptom of the eventual diagnosis.

2. ADVERSE EVENTS OCCURRING SECONDARY TO OTHER EVENTS

In general, adverse events occurring secondary to other events (e.g., cascade events or clinical sequelae) should be identified by their primary cause, with the exception of severe or serious secondary events. However, medically significant adverse events occurring secondary to an initiating event that are separated in time should be recorded as independent events on the Adverse Event eCRF. For example:

- If vomiting results in mild dehydration with no additional treatment in a healthy adult, only vomiting should be reported on the eCRF.

- If vomiting results in severe dehydration, both events should be reported separately on the eCRF.
- If a severe gastrointestinal hemorrhage leads to renal failure, both events should be reported separately on the eCRF.
- If dizziness leads to a fall and subsequent fracture, all three events should be reported separately on the eCRF.

All adverse events should be recorded separately on the Adverse Event eCRF if it is unclear as to whether the events are associated.

3. PERSISTENT OR RECURRENT ADVERSE EVENTS

A persistent adverse event is one that extends continuously, without resolution, between participant evaluation time-points. Such events should only be recorded once on the Adverse Event eCRF. The initial severity of the event should be recorded, and the severity should be updated to reflect the most extreme severity any time the event worsens. If the event becomes serious, the Adverse Event eCRF should be updated to reflect this.

A recurrent adverse event is one that resolves between participant evaluation time-points and subsequently recurs. Each recurrence of an adverse event should be recorded separately on the Adverse Event eCRF.

4. ABNORMAL LABORATORY VALUES

Not every laboratory abnormality qualifies as an adverse event. A laboratory test result should be reported as an adverse event if it meets any of the following criteria:

- Accompanied by clinical symptoms.
- Results in a change in study treatment (e.g., dosage modification, treatment interruption, or treatment discontinuation).
- Results in a medical intervention (e.g., potassium supplementation for hypokalemia) or a change in concomitant therapy.
- Clinically significant in the Investigator's judgment.

It is the Investigator's responsibility to review all laboratory findings. Medical and scientific judgment should be exercised in deciding whether an isolated laboratory abnormality should be classified as an adverse event.

If a clinically significant laboratory abnormality is a sign of a disease or syndrome (e.g., alkaline phosphatase and bilirubin 5 times the ULN associated with cholecystitis), only the diagnosis (i.e., cholecystitis) should be recorded on the Adverse Event eCRF.

If a clinically significant laboratory abnormality is not a sign of a disease or syndrome, the abnormality itself should be recorded on the Adverse Event eCRF, along with a

descriptor indicating if the test result is above or below the normal range (e.g., "elevated potassium", as opposed to "abnormal potassium"). If the laboratory abnormality can be characterized by a precise clinical term per standard definitions, the clinical term should be recorded as the adverse event. For example, an elevated serum potassium level of 7.0 mEq/L should be recorded as "hyperkalemia".

Observations of the same clinically significant laboratory abnormality from visit to visit should not be repeatedly recorded on the Adverse Event eCRF, unless the etiology changes. The initial severity of the event should be recorded, and the severity or seriousness should be updated any time the event worsens.

5. ABNORMAL VITAL SIGN VALUES

Not every vital sign abnormality qualifies as an adverse event. A vital sign result should be reported as an adverse event if it meets any of the following criteria:

- Accompanied by clinical symptoms.
- Results in a change in study treatment (e.g., dosage modification, treatment interruption, or treatment discontinuation).
- Results in a medical intervention or a change in concomitant therapy.
- Clinically significant in the Investigator's judgment.

It is the Investigator's responsibility to review all vital sign findings. Medical and scientific judgment should be exercised in deciding whether an isolated vital sign abnormality should be classified as an adverse event.

If a clinically significant vital sign abnormality is a sign of a disease or syndrome (e.g., high blood pressure), only the diagnosis (i.e., hypertension) should be recorded on the Adverse Event eCRF.

Observations of the same clinically significant vital sign abnormality from visit to visit should not be repeatedly recorded on the Adverse Event eCRF, unless the etiology changes. The initial severity of the event should be recorded, and the severity or seriousness should be updated any time the event worsens.

6. ABNORMAL LIVER FUNCTION TESTS

The finding of an elevated ALT or AST ($> 3 \times \text{ULN}$) in combination with either an elevated total bilirubin ($> 2 \times \text{ULN}$) or clinical jaundice in the absence of cholestasis or other causes of hyperbilirubinemia is considered to be an indicator of severe liver injury. Therefore, investigators must report as an adverse event the occurrence of either of the following:

- Treatment-emergent ALT or AST $> 3 \times \text{ULN}$ in combination with total bilirubin $> 2 \times \text{ULN}$.

- Treatment-emergent ALT or AST > 3 × ULN in combination with clinical jaundice.

The most appropriate diagnosis or (if a diagnosis cannot be established) the abnormal laboratory values should be recorded on the Adverse Event eCRF and reported to the Sponsor immediately (i.e., no more than 24 hours after learning of the event), either as a serious adverse event or a non-serious adverse event of special interest.

7. DEATHS

All deaths that occur during the protocol-specified adverse event reporting period (see Section 5 of [Appendix 2](#)), regardless of relationship to study treatment, must be recorded on the Adverse Event eCRF and immediately reported to the Sponsor.

Death should be considered an outcome and not a distinct event. The event or condition that caused or contributed to the fatal outcome should be recorded as the single medical concept on the Adverse Event eCRF. Generally, only one such event should be reported. If the cause of death is unknown and cannot be ascertained at the time of reporting, “unexplained death” should be recorded on the Adverse Event eCRF. If the cause of death later becomes available (e.g., after autopsy), “unexplained death” should be replaced by the established cause of death. The term “sudden death” should not be used unless combined with the presumed cause of death (e.g., “sudden cardiac death”).

8. PREEXISTING MEDICAL CONDITIONS

A preexisting medical condition is one that is present at the screening visit for this study. Such conditions should be recorded on the General Medical History and Baseline Conditions eCRF.

A preexisting medical condition should be recorded as an adverse event only if the frequency, severity, or character of the condition worsens during the study. When recording such events on the Adverse Event eCRF, it is important to convey the concept that the preexisting condition has changed by including applicable descriptors (e.g., “more frequent headaches”).

9. HOSPITALIZATION OR PROLONGED HOSPITALIZATION

Any adverse event that results in hospitalization or prolonged hospitalization should be documented and reported as a serious adverse event (per the definition of serious adverse event in [Appendix 2](#)), except as outlined below.

An event that leads to hospitalization under the following circumstances should not be reported as an adverse event or a serious adverse event:

- Hospitalization for respite care
- Planned hospitalization required by the protocol

- Hospitalization for a preexisting condition, provided that all of the following criteria are met:
 - The hospitalization was planned prior to the study or was scheduled during the study when elective surgery became necessary because of the expected normal progression of the disease.
 - The participant has not suffered an adverse event.

An event that leads to hospitalization under the following circumstances is not considered to be a serious adverse event, but should be reported as an adverse event instead:

- Hospitalization for an adverse event that would ordinarily have been treated in an outpatient setting had an outpatient clinic been available.

Appendix 4 Clinical Laboratory Tests

The tests detailed in [Table 1](#) will be performed by the central or local laboratory. The results will be entered into the eCRF or loaded electronically.

Protocol-specific requirements for inclusion or exclusion of participants are detailed in Sections [5.1](#) and [5.2](#), respectively, of the protocol.

Additional tests may be performed at any time during the study as determined necessary by the Investigator or required by local regulations.

Table 1 Protocol-Required Safety Laboratory Assessments

Laboratory Assessments	Parameters
Full Hematology	
 [REDACTED]
[REDACTED]	
 [REDACTED]
Full Clinical Blood Chemistry	
 ALT, AST, ALP, GGT, total, direct and unconjugated bilirubin, total protein, haptoglobin, albumin, sodium, chloride, potassium, phosphate, calcium, creatinine, urea, fasting glucose, total cholesterol, triglycerides, CPK, LDH, [REDACTED]
[REDACTED]	
 [REDACTED]
Coagulation	
 Prothrombin time (INR) and activated thromboplastin time (APTT).
Viral Serology	
 HIV (specific tests HIV1 antibody, HIV-1/2 antibody, HIV-2 antibody), hepatitis B surface antigen (HBsAg), hepatitis C virus (HCV) antibody.
Safety Biomarkers	
 [REDACTED] [REDACTED]

Laboratory Assessments	Parameters
Infusion-related reaction blood sample	
 • [REDACTED]
Thyroid Hormones	
 • Thyroid stimulating hormone (TSH) at screening only
Anti-Drug Antibodies	
 • Anti-RO7126209 antibodies in plasma will be determined using a validated ELISA method
Urinalysis	
 • Dipstick: pH, glucose, blood and protein. If there is a clinically significant positive result (may be confirmed by a positive repeated sample), urine will be sent to the laboratory for microscopy and culture. If there is an explanation for the positive dipstick results, it should be recorded and there is no need to perform microscopy and culture. • Microscopic examination (sediment, RBCs, WBCs, casts, crystals, epithelial cells, bacteria), if blood or protein is abnormal.
Alcohol	
 • Urine
Drugs of abuse	
 • Urine tests for (at minimum): amphetamines incl. MDMA, cocaine, opiates, cannabinoids, methadone and benzodiazepines.

The results of each test will be provided electronically or captured into the CRF. Investigators must document their review of each laboratory safety report.

Additional Statistical Considerations for Clinical Laboratory Data

- Standard Reference Ranges and Transformation of Data

Potential analysis considerations for analysing Laboratory data includes the use of Standard Reference Ranges and potential transformation of data for specific lab tests.

In this scenario, Roche standard reference ranges, rather than the reference ranges of the Investigator, can be used for specific parameters. For these parameters, the measured laboratory test result will be assessed directly using the Roche standard reference range. Certain laboratory parameters will be transformed to Roche's standard reference ranges.

A transformation will be performed on certain laboratory tests that lack sufficiently common procedures and have a wide range of Investigator ranges, e.g., enzyme tests that include AST, ALT, and alkaline phosphatase and total bilirubin. Since the standard reference ranges for these parameters have a lower limit of zero, only the upper limits of the ranges will be used in transforming the data.

- Definition of Laboratory Abnormalities

For all laboratory parameters included in this analysis, there exists a Roche predefined standard reference range. Laboratory values falling outside this standard reference range will be labeled “H” for high or “L” for low in participant listings of laboratory data.

In addition to the standard reference range, a marked reference range has been predefined by Roche for these laboratory parameters. The marked reference range is broader than the standard reference range. Values falling outside the marked reference range that also represent a defined change from baseline will be considered marked laboratory abnormalities (i.e., potentially clinically relevant). If a baseline value is not available for a participant, the midpoint of the standard reference range will be used as the participant’s baseline value for the purposes of determining marked laboratory abnormalities. Marked laboratory abnormalities will be labeled in the participant listings as “HH” for very high or “LL” for very low.

Appendix 5

Contraceptive Guidance and Collection of Pregnancy Information

1. DEFINITIONS

- **Woman of Childbearing Potential (WOCBP)**

A woman is considered fertile following menarche and until becoming post-menopausal unless permanently sterile. The definition of childbearing potential may be adapted for alignment with local guidelines or requirements.

- **Women in the following categories are considered to be Woman of Non-Childbearing Potential (WONCBP)**

a) Pre-menarchal

b) Pre-menopausal female with one of the following:

- Documented hysterectomy.
- Documented bilateral salpingectomy.
- Documented bilateral oophorectomy.

Note: Documentation can come from the site personnel's: review of participant's medical records, medical examination, or medical history interview.

c) Post-menopausal female

- A post-menopausal state is defined as no menses for ≥ 12 months without an alternative medical cause other than menopause. A high follicle-stimulating hormone (FSH) level in the post-menopausal range may be used to confirm a post-menopausal state in women not using hormonal contraception or hormonal replacement therapy (HRT). However, in the absence of 12 months of amenorrhea, a single FSH measurement is insufficient.
- Females on HRT and whose menopausal status is in doubt will be required to use one of the non-hormonal highly effective contraception methods if they wish to continue their HRT during the study. Otherwise, they must discontinue HRT to allow confirmation of post-menopausal status before study enrollment.

2 COLLECTION OF PREGNANCY INFORMATION

- **Male participants with partners who become pregnant**

The Investigator will attempt to collect pregnancy information on any male participant's female partner who becomes pregnant while the male participant is in this study (see Section 8.3.5 Pregnancy). This applies only to male participants who receive study treatment.

Attempts should be made to collect and report details of the course and outcome of any pregnancy in the partner of a male participant exposed to study treatment. The

Investigator will record pregnancy information on the Clinical Trial Pregnancy Reporting Form and submit it to the Sponsor within 24 hours of learning of the partner's pregnancy. When permitted by the site, the pregnant partner would need to sign an Authorization for Use and Disclosure of Pregnancy Health Information to allow for follow-up on her pregnancy. If the authorization has been signed, the Investigator should update the Clinical Trial Pregnancy Reporting Form with additional information on the course and outcome of the pregnancy when available. An Investigator who is contacted by the male participant or his pregnant partner may provide information on the risks of the pregnancy and the possible effects on the fetus, to support an informed decision in cooperation with the treating physician and/or obstetrician. The female partner will be followed to determine the outcome of the pregnancy. Information on the status of the mother and child will be forwarded to the Sponsor. Monitoring of the participant's partner should continue until conclusion of the pregnancy. Any termination of the pregnancy will be reported regardless of fetal status (presence or absence of anomalies) or indication for procedure.

3 ABORTIONS

Any spontaneous abortion should be classified as a serious adverse event (as the Sponsor considers spontaneous abortions to be medically significant events), recorded on the Adverse Event eCRF, and reported to the Sponsor immediately (i.e., no more than 24 hours after learning of the event; see Section 5 of [Appendix 2](#)).

Any induced abortion due to maternal toxicity and/or embryofetal toxicity should also be classified as serious adverse event, recorded on the Adverse Event eCRF, and reported to the Sponsor immediately (i.e., no more than 24 hours after learning of the event; see Section 5 of [Appendix 2](#)).

Elective or therapeutic abortion not associated with an underlying maternal or embryofetal toxicity (e.g., induced abortion for personal reasons) does not require expedited reporting but should be reported as outcome of pregnancy on the Clinical Trial Pregnancy Reporting Form.

4 CONGENITAL ANOMALIES/BIRTH DEFECTS

Any congenital anomaly/birth defect in a child born to a female partner of a male patient exposed to study treatment should be classified as a serious adverse event, recorded on the Adverse Event eCRF, and reported to the Sponsor immediately (i.e., no more than 24 hours after learning of the event).

Appendix 6

Statistical Details and Simulation of the Operating Characteristics of the Planned Design for Supporting the Dose-Escalation Recommendations

Statistical Models

Details on the statistical models, methods and algorithms as well as scenarios for evaluating the operating characteristics of the CRM designs are given below.

Model for safety analysis

The relationship between the dose and the probability of observing a DLE will be described by the following two-parameter logistic regression model:

$$\text{logit}(p) = \log\left(\frac{p}{1-p}\right) = \alpha + \beta \log\left(\frac{Dose}{D_{ref}}\right)$$

where p is the probability of observing a DLE at a given dose, α is the log of the odds for p at the reference dose (D_{ref} , here equals to 0.3 mg) and β is the slope of the curve. (detailed discussion about this model parameterization can be found in [Neuenschwander B., Branson M., Gsponer T. Critical Aspects of the Bayesian Approach to Phase I Cancer Trials. Stat Med, 2008; 27:2420-2439.])

[figure not shown]
Since the model will be estimated using a Bayesian framework, priors need to be specified for α and β . Neuenschwander's 'minimally informative prior' will be used (Neuenschwander, 2008). This prior was built on the assumption that the starting dose (0.1 mg/kg) is safe (probability that DLE rate > 0.2 is less than 0.05) and with 10.8 mg/kg, the probability of DLE rate > 0.35 is 0.6.

The resulting bivariate distribution that will be used is:

$$\begin{pmatrix} \alpha \\ \log(\beta) \end{pmatrix} \sim \mathcal{N}\left(\begin{pmatrix} -2.078 \\ -0.948 \end{pmatrix}, \begin{pmatrix} 1.018 & -0.105 \\ -0.105 & 0.499 \end{pmatrix}\right)$$

Figure 1 shows the graph of the chosen prior with 95%-credible interval.

Figure 1. Prior for safety analysis.

Simulations for the operating characteristics

[figure not shown]
Simulations were performed to examine the operating characteristics of the CRM model across some dose-response profiles for safety (DLEs).

For the simulation, the following settings were made:

- Maximum number of cohorts: 6
- Cohort size: For the first 3 dose levels, 4+2 and the last 3 dose levels 6+2
- Decision criterion for safety: $prob(DLE\ rate \geq 30\%) < 0.2$
- The dose grid is (in mg/kg) 0.1 0.2 0.3 0.4 0.5 0.6 0.7 0.8 0.9 1.2 1.5 1.8 2.1 2.4 2.7 3.0 3.6 4.2 4.8 5.4 6.0 6.6 7.2 7.8 8.4 9.0 9.6 10.2 10.8

The simulations were based on a hypothetical 'simulation truth'. Three scenarios based on a logistic regression models, an 'optimistic', a 'realistic' and a 'pessimistic' one, were chosen. The doses, where a DLE probability of 0.3 is achieved under these scenarios are 12 mg/kg, 4 mg/kg, and 2 mg/kg, respectively. Figure 2 below shows a graphical display of these parameters.

Figure 2. Simulation truths for evaluating operating characteristics for safety.

β

Results from the simulations

The first table (Table 1) shows what the next recommended dose is for all possible number of DLEs observed, **assuming no DLEs are observed until the current dose level.**

Table 1: Examination of the chosen safety decision algorithm.

dose	DLTs	next Dose
0.1	0	0.300
0.1	1	0.200
0.1	2	0.001
0.1	3	0.001
0.3	0	0.900
0.3	1	0.700
0.3	2	0.300
0.3	3	0.100
0.9	0	2.700
0.9	1	1.200
0.9	2	0.600
0.9	3	0.400
2.7	0	5.400
2.7	1	4.800
2.7	2	2.100
2.7	3	1.200
5.4	0	10.800
5.4	1	9.600
5.4	2	6.600
5.4	3	3.600

The next table ([Table 2](#)) displays operating characteristics based on 1000 simulations for the three scenarios described in the previous section. D_{max} , denotes the highest dose such that: $\text{Prob}(\text{DLE rate at } D_{max} > 30\%) < 20\%$.

Table 2: Operating characteristics; means and Intervals corresponding to 10 and 90 % quantiles.

Scenario	Proportions of DLEs on active [%]	Dose most often chosen as D _{max}	Observed DLE rate at D _{max} [%]
optimistic	7.3(2.8,12.3β)	4.4 mg/kg	11.7
realistic	9.2(4.8,11.9)	1.6 mg/kg	8.3
pessimistic	13.3(9.5,16.7)	0.8 mg/kg	13.1

Remarks and Conclusions

The proposed CRM design shows a good protection against overdosing and gives reasonable estimates for the mean of the doses as selected as D_{max}. The results in [Table 1](#) have to be interpreted with caution for the lowest doses.

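### Appendix 6 Table 2 contradicts its column headings: the realistic and pessimistic DLE limits fit 42 participants including placebo, not those on active, and two doses given as the most frequent choice are off the simulated grid

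*Combined protocol and SAP*

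**What the plan says.** The settings in Appendix 6 are "Maximum number of cohorts: 6" and, for cohort size (active + placebo), "For the first 3 dose levels, 4+2 and the last 3 dose levels 6+2". The dose grid has 29 values from 0.1 to 10.8 mg/kg. Its middle part reads "1.2 1.5 1.8 2.1 2.4 2.7 3.0 3.6 4.2 4.8 5.4".

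Table 2 is based on 1000 simulations per scenario and gives means with 10% and 90% quantiles. Under "Proportions of DLEs on active" it prints:

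- optimistic: 7.3 (2.8, 12.3)
- realistic: 9.2 (4.8, 11.9)
- pessimistic: 13.3 (9.5, 16.7)

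Under "Dose most often chosen as" Dmax it prints 4.4, 1.6 and 0.8 mg/kg for the same scenarios.

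The Remarks conclude: "The proposed CRM design shows a good protection against overdosing". They add that the design gives "reasonable estimates for the mean of the doses" selected as Dmax. Section 9.3.4 refers to these simulations in support of the model that informs each dose decision.

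**The concern.** A proportion of DLEs on active should have active participants as its denominator. A dose chosen most often should be one the simulation could choose. The printed numbers fail both tests.

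Table 2 is the reported evidence on how the escalation model behaves in a first-in-human study of healthy volunteers. If placebo participants are in the denominator, a reader underestimates the DLE risk of those who receive the drug. If a mean is printed as the most frequent choice, a reader is misled about which dose the design picks. What is at stake is the reported operating characteristics, not the decision rule.

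**Working it through.** **Inputs** (all Appendix 6): six cohorts, 4+2 three times and then 6+2 three times. Active: 3 × 4 + 3 × 6 = 30. Placebo: 6 × 2 = 12. Total: 42.

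**1. Dose column.** On the grid, 4.2 is followed by 4.8 and 1.5 by 1.8. So 4.4 and 1.6 are absent; 0.8 is present. Two of the three entries cannot be modes of a grid-valued choice.

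**2. DLE limits.** If every run stops at a whole cohort, the active total is 4, 8, 12, 18, 24 or 30.

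| Printed limit | Nearest values with 30 active | With 42 in all |
|---|---|---|
| 4.8 (realistic, 10%) | 1/30 = 3.3, 2/30 = 6.7 | 2/42 = 4.76 |
| 11.9 (realistic, 90%) | 3/30 = 10.0, 4/30 = 13.3 | 5/42 = 11.90 |
| 9.5 (pessimistic, 10%) | 2/30 = 6.7, 3/30 = 10.0 | 4/42 = 9.52 |
| 16.7 (pessimistic, 90%) | 5/30 = 16.7 | 7/42 = 16.67 |

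The last limit does not discriminate; the other three do. None of the three is k/n for the smaller active totals either. If cohort size followed dose level instead of cohort order, active totals could be any even number from 4 to 36, and still none fits. Among the reachable totals including placebo (6 to 48), only 42 gives all three. Interpolated quantiles for 1000 runs (weights 0.9 and 0.1) between neighbouring active-only values do not round to them.

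The optimistic limits fit neither reading. 2.8 is 1/36, which is reachable only if cohort size follows dose level, and 12.3 fits no reachable total.

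**3. Size.** Let m be the printed mean, p the placebo DLE rate (assumed) and all six cohorts be dosed. The rate on active is a = (42m − 12p)/30. For the pessimistic row, 42 × 0.133 = 5.586:

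- p = 0: 5.586/30 = 18.6% (1.40-fold)
- p = 2%: (5.586 − 0.24)/30 = 17.8% (1.34-fold)
- p = 5%: (5.586 − 0.60)/30 = 16.6% (1.25-fold)

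**4. Cross-check by re-simulation.** This used the printed prior, grid, 20% criterion and cohort sizes, with increments read from Table 1 ("Examination of the chosen safety decision algorithm"). True slopes of 1 to 2 were assumed because Figure 2 is not visible. There were no placebo DLEs and 1,000 runs per setting.

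| Row | Printed | Over all participants | Over active |
|---|---|---|---|
| Pessimistic | 13.3 (9.5, 16.7) | 12.9–13.5 (9.5, 16.7) | 18.1–18.8 (13.3, 23.3) |
| Realistic | 9.2 (4.8, 11.9) | 10.9–11.0 (7.1, 14.3) | see below |

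More than 99% of pessimistic runs dosed all six cohorts. With 2–5% placebo DLEs, the upper pessimistic limit over all participants becomes 19.0 instead of 16.7. In a smaller run (300 per setting, slopes 0.5 to 2), the realistic mean was 14.8 to 17.4 on active and 10.6 to 12.4 over all. That row is therefore not reproduced, though dividing by 42 comes closer.

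**5. How placebo was handled.** Reconstructing the 20 rows of Table 1 matches 15 with active participants only. It matches 17 if two placebo participants per cohort, without DLEs, are entered at 0.001 mg/kg, an off-grid value that Table 1 prints as a next dose. It matches 6 if placebo participants are counted as active. This suggests, but does not prove, that placebo participants sit in the simulated data as a dose level.

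**The case against.** The strongest reply is that a denominator of 42 does not show that 12 of the 42 were on placebo. If the simulation dosed every participant with drug, 13.3% would be a true active rate from a mis-sized simulation, with no dilution. A run with 42 active, slope 1 and a stricter 5% rule gave 12.4 (9.5, 16.7). But that leaves the stated 20% rule; under the stated rule the all-active version gave about 18%, not 13.3%. It would also contradict the stated 4+2 and 6+2 cohorts. What stands is that the cause is not proven.

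The reconstruction also misses much of the table. At slopes 1 to 2, mean Dmax was about 1.5–1.7, 3.2–3.6 and 8.3–10.0 mg/kg, roughly twice the printed 0.8, 1.6 and 4.4. If the printed doses are means, the sponsor's runs chose lower doses, and the match on the pessimistic DLE row is weaker support than it looks. The grid and fraction checks do not depend on the reconstruction.

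The last column of Table 2, the observed DLE rate at Dmax, prints 8.3% and 13.1%, close to the realistic and pessimistic means. It is a rate at one dose, and no denominator is stated for it, so it does not settle the question.

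On the dose column, the caption mentions means, the definition of Dmax is not explicitly limited to the grid, and Table 1 prints an off-grid value. A labelling slip is therefore likely. It still leaves the heading wrong.

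The practical effect is limited: Section 9.3.4 lets clinical judgment override the model.

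**Conclusion.** The concern holds. Under the stated settings, 4.8, 9.5 and 11.9% cannot be proportions of active participants, and 4.4 and 1.6 mg/kg cannot be most frequent grid choices. Heading, settings or figures must be wrong.

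The likeliest reading of the realistic and pessimistic rows is division by active plus placebo. The pessimistic mean on active would then be about 16.6 to 18.6%, against 13.3% printed. The upper figure assumes no placebo DLEs; the whole range assumes six full cohorts and placebo DLE rates of 0 to 5%.

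That the dose column holds means is suggested by the Remarks, not established. Confidence in the explanation is medium; confidence in the mismatch itself is high. The escalation rule is not affected.

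**What to change.** From the existing simulation output:

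1. State the denominator of the DLE column and recompute it as DLEs on active divided by active participants, in all three rows.
2. Check the optimistic limits (2.8, 12.3) against that output.
3. Report the mode of Dmax, which should be a grid dose, and its mean in separately labelled columns.
4. Re-read the overdosing conclusion against the corrected figures and adjust its wording if needed.

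This is re-summarising and relabelling, with no design change and, provided the stored output is consistent, no new simulation. The realistic and pessimistic DLE percentages would probably become less favourable.
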